#### Background

Postoperative urinary retention (POUR) is a significant postoperative complication in 14-16% of all surgeries (Kowalik) and 21-50% following female pelvic reconstructive surgery (Ripperda). POUR is associated with increased risk of urinary tract infection and healthcare costs (Hooten) as well as decreased patient satisfaction (Kenton).

The bladder neck and urethra are rich in  $\alpha$ -adrenergic receptors. One potential mechanism by which POUR occurs following female pelvic reconstructive surgery is disruption of the local autonomic nervous system, increasing sympathetic drive to the bladder outlet and inhibiting urethral relaxation and bladder emptying. The prophylactic use of  $\alpha$ -AR antagonists before the onset of symptoms may decrease the incidence of POUR after urologic and colorectal surgery in men (Ghuman, Akkoc, Poylin, Claney). Recently, a retrospective matched cohort study by Chapman et al. showed a significantly decrease risk of POUR with the use of tamsulosin following female pelvic reconstructive surgery. In this study, active voiding trials were performed on postoperative day 1 for the tamsulosin group. In a follow-up double-blinded randomized controlled trial, a 10-day course of tamsulosin started 3 days preoperatively vs. placebo showed a reduction in POUR from 24.6% in the placebo group to 8.7% in the tamsulosin group (Chapman). The voiding trials in this study were performed on postoperative day 1.

With enhanced recovery after surgery protocols, same-day discharge has become a common phenomenon with female pelvic reconstructive surgery. It is safe and cost effective for patients with no increase in postoperative complications as compared to an overnight stay (Schiavone, Jennings, Carter-Brooks). Same day hospital discharge with voiding trials performed on the day of procedure, however, may be associated with even higher rates of acute POUR. In our unit, at least 50% of women undergoing multicompartment native tissue vaginal repair, who are discharged on the same day, have to perform either self-catheterization or have an indwelling Foley catheter which increases patient burden and risk of UTIs. It may also decrease overall patient satisfaction.

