# Secondary Aim(s):

- To compare the mean total number of days of postoperative catheterization, incidence of delayed urinary retention and urinary tract infection rates up to 6 weeks post-surgery between groups
- (2) To compare ED visits and serious adverse events, as classified by Clavien-Dindo, between groups
- (3) To compare patient level of satisfaction with voiding function immediately prior to hospital discharge and at 1 week post-procedure.

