#### Secondary:

To compare the following between the two groups:

- 1. Postoperative urinary tract infection rates (up to 6 weeks post-surgery)
- Incidence of delayed urinary retention (defined as PVR > 150 ml up to 6 weeks post-surgery)
- 3. ED visits and serious adverse events within 30 days post procedure
- 4. Total number of days of catheterization
- 5. Patient level of satisfaction with voiding/bladder function immediately prior to hospital discharge: Very dissatisfied, moderately dissatisfied, slightly dissatisfied, neutral, slightly satisfied, moderately satisfied, very satisfied

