#### Study Intervention –

10 pills of each IP and placebo will be placed in identical coded containers and stored in a locked area in the clinic. Instructions for IP usage will be provided to subjects for 10 days of usage as 0.4 mg qd by PO route starting 5 days prior to day of surgery and continued for a total 10 days. The research manager will be the only member of the study team who has the research key designating which containers are IP versus placebo.

On postoperative day 0 after recovery from anesthesia, each patient will have their bladder emptied using the indwelling Foley and their bladder will then be retrograde-filled with 300 cc of normal saline and given 30 minutes to void. A postvoid residual volume<150 cc will be considered a success of the voiding trial. If the voiding trial was considered failed, the patient will have a foley catheter reinserted and the patient will be instructed to remove the catheter at home after having a bowel movement. If they are unable to void at home within 4 hours of catheter removal, they will return to the Wake Forest Urology clinic for self-catheter teaching.

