### Power analysis

For a superiority study, if we assume 5% significance level and 80% power with internal audit rates of POUR of 24.3% for the control group and expecting 2.9% for the tamsulosin group (Chapman), then total sample size would be approximately 74 with n= 37 in each group. Accounting 20% non-compliant and dropout rate, we expect to enroll 88 patients total with 44 in each group. Power calculations done with sealedenvelope.com

Statistical analysis will be performed using IBM SPSS Statistics 24 or similar program.

Baseline and demographic data will be reported using standard descriptive methods. Scores of questionnaires (age, race, BMI, insurance, smoking y/n) and clinical evaluations (menopausal status, vaginal atrophy y/n, estrogen use, type of surgery etc.) will be calculated appropriately. Outcomes will be presented as number with proportion for categorical data and mean and standard deviation (in case of normally distributed data) or median with interquartile range (in case of not normally distributed data). Comparisons within groups will be done for numerical data using either paired t-test (in case of normally distributed data) or Wilcoxon signed rank test (in case of not normally distributed data) and Fisher exact test or Mcnemar for categorical data. Between-group comparisons will be done using either unpaired t-test (in case of normally distributed

data) or Mann-Whitney U test (in case of not normally distributed data) and Chi-square test for categorical data.

	Baseline	Day of surgery	Week 1 post- operative visit	Week 6 postoperative visit
Consent	x			
Dispense IP	x			
Voiding trial		x		
PVR	x	x	х	x
UA	x		х	x
Level of satisfaction with voiding function (1-7)	x	x	x	
Return IP bottle			x	

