# Postop parameters

- Active voiding trial PVR on POD 0
- Day of bladder function return
- UTI within 6 weeks
- Persistent urinary retention > 2 weeks
- Delayed urinary retention (PVR > 150 after passing 1st trial of void)
- Emergency Room visit/evaluation

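### The secondary aim is a difference in mean catheter days, but the normality rule replaces it with medians that are almost surely 0 in both arms and a rank test driven mainly by who was catheterised

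*Combined protocol and SAP*

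**What the plan says.** The Secondary Aims section states the target as a mean: "To compare the mean total number of days of postoperative catheterization". The secondary outcome list repeats the variable without naming a summary measure: "Total number of days of catheterization".

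The Power analysis section holds the only analysis rule. Numerical outcomes are described by "mean and standard deviation (in case of normally distributed data) or median with interquartile range (in case of not normally distributed data". Groups are compared by unpaired t-test if the data are normal, and otherwise by "Mann-Whitney U test (in case of not normally distributed data) and Chi-square test for categorical data". Catheter days have no rule of their own.

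Under Study Intervention, the Foley is reinserted only after a failed day 0 voiding trial, and then "the patient will be instructed to remove the catheter at home after having a bowel movement". Women who cannot void after removing it return to be taught self-catheterisation. Appendix A also collects "Day of bladder function return" and records delayed retention in women who passed the first trial.

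**The concern.** A woman who passes on day 0 goes home without a catheter and scores 0 unless she is catheterised later. If most women pass, the distribution is a large spike at 0 with a short right tail. No normality check would accept that, so the choice of branch is settled in advance: medians and a rank test. The quantity named in the aim then drops out of the analysis.

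This matters because the Background gives catheter burden as a reason for the trial, and this outcome is the one meant to measure how long that burden lasts. A report of 0 against 0 days with a small p-value would not tell readers how many catheter days were saved. They might also take the p-value as evidence about duration when it is mostly evidence about incidence.

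**Working it through.** **Inputs from the documents.** Retention 24.3% (control) and 2.9% (tamsulosin), 5% significance, 80% power and 37 per arm (Power analysis). Published trial rates of 24.6% and 8.7%, and a local figure of "at least 50% of women undergoing multicompartment native tissue vaginal repair" going home with a catheter or self-catheterising (Background).

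**Assumptions, not in the documents.** Home Foley removal falls evenly on days 1 to 3 (mean 2). A fraction q of women who fail then self-catheterise for x further days. The central case is q = 25%, x = 7; the range runs from q = 0 to q = 50%, x = 14. Tests are two-sided at 5%.

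**1. The plan's own figure.** Unpooled two-proportion formula: n = (1.960 + 0.842)² × [0.243 × 0.757 + 0.029 × 0.971] / (0.243 − 0.029)² = 36.35, rounded up to 37 per arm. The stated size reproduces. The documents give no figure for catheter days.

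**2. Share of zeros.** 1 − 0.243 = 75.7% of placebo and 1 − 0.029 = 97.1% of tamsulosin women score 0 if day 0 failures are the only source of catheter days. The non-normal branch applies.

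**3. Medians.** With 37 women the placebo median exceeds 0 only if 19 or more are catheterised. The binomial probability is 0.03% at 24.3%, 0.04% at 24.6% and 50% at 50%. For tamsulosin at 2.9% it is negligible. Suppose 5% of women who pass are catheterised later. The placebo share becomes 0.243 + 0.757 × 0.05 = 28.1%, and the probability is still only 0.2%. If day 0 were counted as a day for everyone, both medians would rise by the same amount.

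**4. Does the rank test respond to duration?** True mean difference = rate difference × (2 + q × x):

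| Duration assumption | True mean difference, days | Mann-Whitney power |
|---|---|---|
| q = 0 | 0.214 × 2 = 0.43 | 82–83% |
| q = 25%, x = 7 | 0.214 × 3.75 = 0.80 | 82–83% |
| q = 50%, x = 14 | 0.214 × 9 = 1.93 | 82–83% |

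The mean saving changes more than fourfold and the power does not move.

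**5. Overlap with the primary test.** Simulated share of trials in which Mann-Whitney on days and the uncorrected chi-square on day 0 failure agree at 5%, at the planned rates and 37 per arm:

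| Women who pass but are catheterised later (assumed, both arms) | Same verdict |
|---|---|
| 0% | about 97% |
| 2% | about 87% |
| 5% | about 75% |
| 10% | about 64% |

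The central duration assumption applies. With no later catheterisation, geometric, lognormal and Poisson durations give similar agreement, about 98%.

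**6. One data set.** Take 9 of 37 against 1 of 37 failures, with 28 and 3 catheter days in total. The means are 28/37 = 0.76 and 3/37 = 0.08, a difference of 0.68 days. The rule would report 0 (0–0) in both arms with Mann-Whitney p = 0.0073, beside a primary chi-square p = 0.0065. The 0.68 days would not appear.

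**The case against.** Four points count against a stronger version.

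*A reader might infer that the rank test simply repeats the primary endpoint.* That needs nobody who passes on day 0 to be catheterised later. The protocol expects such events: delayed retention is a secondary outcome and a stated reason for postoperative dosing. The documents give no rate, and step 5 shows agreement falling quickly as the rate rises. The supportable statement is that the test mostly reflects who was catheterised.

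*A reader might infer that Mann-Whitney would hide a harm.* One can construct cases with equal mean days, such as 24.6% × 3.75 = 0.92 against 8.7% × 10.6 = 0.92, in which it favours tamsulosin in about 35% of trials. But that requires about 86% of tamsulosin failures to self-catheterise for 10 further days, against 25% for 7 days on placebo. At 8.7% of 37 that concerns about three women. Nothing in the documents suggests this pattern, and fewer tamsulosin women would truly have needed a catheter.

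*The plan is not blind to duration.* It reports the interquartile range with the median, and the placebo upper quartile exceeds 0 in about 40% of trials at 24.3%. The day bladder function returned and retention beyond two weeks are both collected. This stands, but none of it yields the mean.

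*Replacing the rank test is a choice, not a correction.* A permutation test of means has about 66% power against 83% at the planned rates. This stands, so the recommendation concerns what is reported and does not require a different test.

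**Conclusion.** The concern holds in a limited form. At the planned rates the plan never estimates the quantity in its own secondary aim. That follows from the text and the share of zeros, with no assumption about duration. Both medians are 0 in at least 99.9% of trials at 37 per arm, provided catheter days come only from day 0 failures. If the placebo failure rate were 50%, this would happen in only about half of trials, but the mean would still go unreported.

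That the rank test carries little information on duration is well supported. How closely it tracks the primary result depends on an unknown rate of later catheterisation: about 97% agreement at 0%, down to about 64% at 10%.

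This is one secondary outcome. The primary test and the sample size are untouched, and the documents do not support a claim that the planned test would reverse the direction of benefit.

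**What to change.** In the Power analysis section, exempt catheter days from the normality rule for reporting:

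- For all randomised women with a voiding trial, counting 0 for those never catheterised after it, report mean days per arm and the difference in means with a 95% confidence interval (bootstrap or Welch).
- Beside it, report the number catheterised in each arm and, descriptively only, the days among those women.
- Mann-Whitney may stay as a supporting test, described as largely reflecting incidence. A permutation test of means is optional, given its lower power.

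**Cost.** Text only. The total is already a planned outcome, so no patients or visits are added. The interval will be wide because a few long catheterisations dominate the variance. At 37 per arm a Welch interval covered 91–95% in the scenarios simulated, so it may fall slightly short of its nominal level.

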# Specific Aims

# Primary Aim(s):

(1) To compare rates of POUR following an active voiding trial on postoperative day 0 between women undergoing multicompartment, native tissue vaginal repair that received perioperative tamsulosin versus women that received placebo

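### For within-group categorical comparisons the plan offers Fisher's exact test or McNemar with no rule for choosing, but only McNemar tests paired change

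*Combined protocol and SAP*

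**What the plan says.** All the analysis rules stand in the paragraphs after the sample-size statement in the Power analysis section.

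- **Within groups, numerical data:** "Comparisons within groups will be done for numerical data using either paired t-test" or, for non-normal data, the Wilcoxon signed-rank test.
- **Within groups, categorical data:** "Fisher exact test or Mcnemar for categorical data". Nothing says when each is to be used.
- **Between groups, categorical data:** "Chi-square test for categorical data".

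The aims and outcomes are mostly between-group. The primary aim is "To compare rates of POUR following an active voiding trial on postoperative day 0 between women" on tamsulosin and women on placebo. The secondary outcomes list opens with "To compare the following between the two groups". Secondary aim 3, on satisfaction with voiding before discharge and at 1 week, is the one aim that does not name the two groups.

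The visit table in the same section schedules repeated measurements: satisfaction (scored 1 to 7) at baseline, day of surgery and week 1; urinalysis at baseline, week 1 and week 6; and post-void residual at all four time points.

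**The concern.** A within-group comparison here sets the same women at one time against themselves at another. The paired t-test and signed-rank test in the same sentence leave little room for another reading. Fisher's exact test assumes two independent samples, so it does not answer a before/after question.

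It could be misapplied in two ways. The two time points could be entered as if they were separate groups of women, which ignores the pairing. Or the before-by-after cross-table could be tested, which asks whether the two measurements are associated, not whether the proportion changed.

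For numerical data the plan gives a rule for choosing (normal or not). For categorical data it gives none, so the analyst may pick the test that does not fit. At stake is any before/after categorical p-value the trial reports.

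**Working it through.** **Sample size, used only to set n for the illustration.** Inputs from Power analysis: 24.3% and 2.9%, 5% significance, 80% power. Sidedness is not stated; two-sided is assumed. With unpooled variances:

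n = (1.960 + 0.842)² × [0.243 × 0.757 + 0.029 × 0.971] / (0.243 − 0.029)² = 7.849 × 0.2121 / 0.0458 = 36.35, rounded up to 37 per group.

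This reproduces the plan's 37. The point does not depend on it.

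**Illustration.** The documents give no before/after categorical counts, so these are assumptions: 37 women, 5 positive before, 11 after. Let k be the number of baseline-positive women who become negative. The paired table is then: positive at both times 5 − k; positive then negative k; negative then positive 6 + k; negative at both times 26 − k.

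- Exact McNemar uses only the women who changed: p = 2 × Σ C(6 + 2k, i) / 2^(6 + 2k), summed over i = 0 to k. For k = 0 this is 2/64 = 0.031. For k = 1 it is 2 × (1 + 8)/256 = 0.070.
- Fisher as independent samples compares 5/37 with 11/37, whatever k is.
- Fisher on the cross-table tests association in the paired table.
- Correlation is φ = [(5 − k)(26 − k) − k(6 + k)] / √(5 × 32 × 11 × 26). For k = 0 this is 130/213.9 = 0.61.

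| k | φ | Exact McNemar p | Fisher, independent samples p | Fisher, cross-table p |
|---|---|---|---|---|
| 0 | 0.61 | 0.031 | 0.157 | 0.001 |
| 1 | 0.43 | 0.070 | 0.157 | 0.021 |
| 2 | 0.26 | 0.109 | 0.157 | 0.144 |
| 3 | 0.09 | 0.146 | 0.157 | 0.623 |
| 4 | −0.08 | 0.180 | 0.157 | 1.000 |
| 5 | −0.26 | 0.210 | 0.157 | 0.295 |

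The net change is 6 women in every row. Independent-samples Fisher cannot see k. Its p-value is too large where the correlation is positive and too small where it is negative. The cross-table p-value follows the strength of association and not the change.

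**Error rates.** Simulated paired data, 37 pairs, 20,000 data sets per setting, assumed 50% positive at both times (no true change), nominal 5%:

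| Correlation | Exact McNemar | Fisher, independent samples | Fisher, cross-table |
|---|---|---|---|
| −0.3 | 2.9% | 5.1% | 40% |
| 0 | 2.9% | 2.6% | 4.0% |
| 0.3 | 2.6% | 0.8% | 40% |
| 0.5 | 2.2% | 0.2% | 86% |
| 0.6 | 1.8% | 0.06% | 97% |

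For an assumed true change from 30% to 50%, power at correlations 0.3, 0.5 and 0.6 is 44%, 58% and 70% for McNemar, against 30%, 26% and 23% for Fisher as independent samples.

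**Where it could apply.** The primary aim and the secondary outcomes list are between-group, so they fall under the chi-square, t-test or Mann-Whitney sentence. Aim 3 names two time points and no groups. If it is read as within-group, and the seven labelled levels are treated as categorical, it falls under the faulty phrase. Neither named test then suits it, because McNemar in its usual form is for a two-by-two table.

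**The case against.** The strongest reply is that McNemar, the correct paired test for binary data, is named in the same phrase, so no p-value is wrong unless an analyst passes over it. That stands, and it limits the point to an unqualified choice. A reader might infer that the plan prescribes Fisher for paired data and that its before/after results will be wrong; the text does not say so.

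A second reply is that no planned categorical analysis is shown to be affected. This largely stands. No within-group hypothesis is stated. Urinalysis is repeated, but no section defines a positive result as a binary endpoint or plans a before/after comparison of it; urinary tract infection is a single outcome up to 6 weeks, compared between groups. Aim 3 is the only candidate, and the secondary outcomes list treats pre-discharge satisfaction as between-group. A 1-to-7 score might also be analysed under the numerical branch, where signed-rank is already available.

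A third reply is that the k = 0 row is the most favourable contrast for those margins. That also stands, and is why the whole range is given: from k = 2 onward all three p-values exceed 0.05. Nor may a reader infer that false positives would be inflated in general. With positive correlation, independent-samples Fisher errs the other way; only the cross-table use inflates rejection strongly, and the documents do not say that use is intended.

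Finally, one might infer that Fisher was put in the wrong sentence and belongs in the between-group one. The documents do not say this, and the change is not a clear correction. At the plan's rates the expected number with retention is 37 × (0.243 + 0.029)/2 = 5.03 per arm, just above the usual limit of 5. For rarer events there is a trade-off: with 37 to 44 per arm and event rates of 2% to 14%, the type I error of uncorrected chi-square is about 0.6% to 5.9%, against 0.01% to 2.4% for Fisher.

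**Conclusion.** The sentence is wrong as written, and the consequence is minor. Fisher's exact test is listed as an equal alternative to McNemar for paired categorical data, it does not test paired change, and no other section corrects this. That the data are paired is inferred from the companion tests in the sentence, which is a sound reading.

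The sample size, the primary comparison and the between-group secondary outcomes are unaffected. The exposure is limited to unspecified before/after comparisons and, on one reading, the satisfaction aim. The p-values and error rates above rest on assumed counts, proportions and correlations. They show the direction and possible size of the discrepancy and do not predict this trial's results.

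**What to change.** In the within-group sentence of the Power analysis section:

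1. Delete Fisher's exact test.
2. Name the exact McNemar test for paired binary data.
3. Name the Wilcoxon signed-rank test for any paired comparison of the 7-level satisfaction score.

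The between-group sentence need not change on this account.

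The cost is an edit to one sentence. Sample size, visits, data collection and the primary analysis stay as they are.

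### Satisfaction is scheduled at baseline, but no between-arm test named in the plan uses that score, so some precision on a secondary outcome is given up

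*Combined protocol and SAP*

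**What the plan says.** Satisfaction with voiding is a stated aim. Item 3 of the Secondary Aim(s) is to compare "patient level of satisfaction with voiding function immediately prior to hospital discharge and at 1 week post-procedure". The secondary list under Outcomes includes the discharge score, on seven ordered levels, among the between-group comparisons.

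The calendar of events has a row "Level of satisfaction with voiding function (1-7") marked at baseline, day of surgery and week 1, and Data Collection and Management says that data are collected at each visit in that calendar.

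The analysis text under Power analysis is generic and does not name satisfaction. For within-arm comparisons it says: "Comparisons within groups will be done for numerical data using either paired t-test (in case of normally distributed data"), with Wilcoxon signed rank as the non-normal alternative and Fisher or McNemar for categorical data. For comparisons between arms it says: "Between-group comparisons will be done using either unpaired t-test (in case of normally distributed" data), with Mann-Whitney U as the non-normal alternative and chi-square for categorical data. Baseline data are otherwise to be summarised descriptively. No ANCOVA, regression, ordinal model, covariate or change score is named anywhere.

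**The concern.** A baseline measurement of a named outcome is scheduled but has no stated role in the randomised comparison of that outcome. In a trial this small, conditioning on baseline is a cheap way to sharpen a patient-reported comparison. It should be chosen in advance, because a decision to adjust taken after unblinding would look data-driven.

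The paired tests raise a second, milder issue. Surgery itself may change satisfaction with voiding in both arms. A significant change in one arm beside a non-significant change in the other says nothing reliable about tamsulosin against placebo. The plan does not say which of its tests answers the satisfaction aim, so that misreading is left open.

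**Working it through.** **Inputs from the documents.** Power analysis gives a 5% significance level, 80% power, POUR rates of 24.3% (control) and 2.9% (tamsulosin), 37 evaluable women per arm and 44 enrolled per arm. No effect size, SD or correlation is given for satisfaction.

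**Assumed.** r, the correlation between baseline and follow-up satisfaction, is taken from 0 to 0.7.

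**1. The plan's own figure.** It relates to POUR, and is checked only to confirm the sample size used below. For two proportions with unpooled variance and a two-sided test:

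n = (1.960 + 0.842)² × [0.243 × 0.757 + 0.029 × 0.971] / (0.243 − 0.029)² = 36.35 per arm.

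This rounds up to 37, so "total sample size would be approximately 74 with n= 37 in each group" is reproduced. It was not derived for satisfaction.

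**2. Unadjusted comparison of satisfaction.** By normal approximation, the detectable difference is 2.802 × √(2/37) = 0.65 SD. Using the t distribution it is 0.66 SD. With all 44 per arm, the normal approximation gives 0.60 SD.

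**3. ANCOVA on the 1-7 score.** The residual variance is multiplied by 1 − r², so the detectable difference is 0.660 × √(1 − r²). The equivalent number per arm is 37 / (1 − r²). The last column is the power for the difference that the unadjusted test detects with 80% power (normal approximation).

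| r (assumed) | Variance reduction | SE reduction | Detectable difference | Equivalent n per arm | Power |
|---|---|---|---|---|---|
| 0.1 | 1% | 0.5% | 0.66 SD | 37.4 | 80.4% |
| 0.3 | 9% | 4.6% | 0.63 SD | 40.7 | 83.6% |
| 0.5 | 25% | 13.4% | 0.57 SD | 49.3 | 89.9% |
| 0.7 | 49% | 28.6% | 0.47 SD | 72.5 | 97.5% |

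The SE reductions are the same with 44 per arm.

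**4. Cost if baseline is uninformative.** At r = 0, the variance rises by the factor 1 + 1/(2 × 37 − 4) = 1 + 1/70, about 1.4%.

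**5. A change score is not an equivalent fix.** Its variance is 2(1 − r) times that of the unadjusted score: 1.4 at r = 0.3, 1.0 at r = 0.5 and 0.6 at r = 0.7. Below r = 0.5 it is less precise than ignoring baseline.

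**6. Proportional-odds model.** The 1 − r² factor does not carry over to the log odds ratio, because adjusting for a prognostic covariate moves that ratio away from zero and raises its SE. A small simulation used 37 per arm, seven levels, a latent effect of 0.5 SD and 150 runs per value of r (all settings assumed). The mean SE of the log odds ratio went from 0.423 to 0.430 at r = 0.3 and from 0.423 to 0.435 at r = 0.5. Mean z at r = 0.5 still rose from 2.09 to 2.33. So power improves, but the interval on the log-odds scale does not narrow.

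**The case against.** The strongest reply is that nothing here is invalid. Allocation is randomised, so an unpaired t-test or Mann-Whitney test is a legitimate comparison, and chance baseline differences are already reflected in its standard error. A reader might infer that the planned comparison is biased. The documents do not support that, and this part of the reply stands in full.

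The gain may also be slight. The discharge score is taken on the day of the voiding trial, and under Study Intervention women who fail have a Foley catheter reinserted. The Background itself suggests that catheter use may lower satisfaction. Early scores may therefore owe more to the voiding trial than to how a woman felt before repair. Below r = 0.3 the SE falls by less than 5%. Nor do the documents give a baseline distribution, so wide variation at baseline cannot be assumed. This stands as a limit on size, and is why low values of r are shown.

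A reader might also take it as stated that baseline satisfaction is used only in the paired tests, or that those tests will be offered as evidence of effect. The text says neither. It does not name satisfaction or the time points being paired, and it specifies between-group tests separately. What can be said is narrower: no named between-arm test uses baseline, and the paired tests are the only named tests that could.

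Finally, baseline collection rests on the calendar row. The Pre-Assessment list and Appendix A omit satisfaction, and Post-Surgery Assessments lists it only after surgery. Because Data Collection and Management ties collection to the calendar, it is reasonable to treat the baseline score as planned, but the sections should agree.

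**Conclusion.** The point holds as a low-cost improvement to one secondary outcome. The loss is precision. With ANCOVA and 37 per arm, the detectable difference is essentially unchanged at r = 0.1 and falls from 0.66 SD to 0.63, 0.57 or 0.47 SD at r = 0.3, 0.5 or 0.7. Against that stands a cost of about 1.4% in variance if r = 0. These figures assume that the 1-7 score is analysed as a numerical score, that baseline is collected as the calendar shows, and that r lies in the range used; the documents do not fix r. They do not describe the log-odds interval of an ordinal model. The POUR analysis and the sample size are unaffected.

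**What to change.** - For satisfaction at discharge and at week 1, pre-specify ANCOVA on the 1-7 score with treatment and baseline satisfaction as terms, and report the adjusted difference with a 95% CI. This also settles whether the item is handled as numerical or categorical.
- If the ordinal scale is preferred, a proportional-odds model with the same two terms is an acceptable alternative. It gains power but does not narrow the log-odds interval, and it adds the proportional-odds assumption. Do not substitute a plain change score.
- State that within-arm paired tests are descriptive and are not evidence of a treatment effect.
- Add satisfaction to the Pre-Assessment list so that it matches the calendar.

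The cost is a few sentences of wording. No measurement is needed beyond those already in the calendar.
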